## **VERSION HISTORY**

| Version | PDAP Date | Change         | Rationale        |
|---------|-----------|----------------|------------------|
| 1       |           | Not Applicable | Original version |
|         |           |                |                  |

# LIST OF ABBREVIATIONS

| ADaM             | Analysis Data Model                                 |
|------------------|---|
| ANOVA            | Analysis of variance                                |
| AUC              | Area under the concentration-time curve             |
| BLQ              | Below the limit of quantitation                     |
| Cavg             | Average concentration                               |
| CI               | Confidence interval(s)                              |
| CKD              | Chronic kidney disease                              |
| CL               | Clearance   |
| CL               | Apparent clearance (CL/F)                           |
| C max | Maximum concentration                               |
| $C_{min}$        | Minimum concentration                               |
| CWRES            | Conditional weighted residuals                      |
| CYP              | Cytochrome P450                                     |
| EMA              | European Medicines Agency                           |
| EPO              | Erythropoietin                                      |
| ESRD             | End-stage renal disease                             |
| ETA              | Interindividual random effect                       |
| F1               | Relative bioavailability                            |
| FDA              | Food and Drug Administration                        |
| FOCE-I           | First order conditional estimation with interaction |
| GFR              | Glomerular filtration rate                          |
| GOF              | Goodness-of-fit                                     |
| HD               | Haemodialysis                                       |
| Hgb              | Haemoglobin   |
| НІ               | Hepatic impairment                                  |
| HIF              | Hypoxia-inducible factor                            |
| IIV              | Interindividual variability                         |
| IMP              | Importance sampling                                 |
| IOV              | Inter-occasion variability                          |
| IPRED            | Individual predicted values                         |
| IWRES            | Individual weighted residuals                       |
| ka               | Absorption rate constant                            |
| KM               | Dose amount at half-maximal absorption              |
| ND               | No dialysis   |
| NONMEM           | Nonlinear mixed-effects modelling                   |
| NPC              | Numerical predictive check                          |
| NPDE             | Normalized prediction distribution errors           |
| OFV              | Objective function value                            |
| pcVPC            | Prediction-corrected visual predictive check        |
| PD               | Peritoneal Dialysis                                 |
| PHI              | Prolyl hydroxylase inhibitor                        |

| PI   | Prediction interval(s)  |
|------|---|
| PK   | Pharmacokinetic(s)  |
| PRED | Population predicted values                                   |
| PsN  | Perl-speaks-NONMEM  |
| QC   | Quality control   |
| QD   | Once daily  |
| Qx   | Apparent inter-compartmental clearance (Qx/F)                 |
| RSE  | Relative standard errors                                      |
| RUV  | Residual unidentified variability                             |
| SAEM | Stochastic approximation expectation maximization             |
| SAS  | Statistical Analysis System                                   |
| SDTM | Study Data Tabulation Model                                   |
| SE   | Standard error(s)   |
| SIR  | Sampling importance resampling                                |
| TIW  | Three times a week  |
| Tr   | Transit compartment   |
| US   | United States   |
| Vmax | Maximal absorption rate                                       |
| VPC  | Visual predictive check                                       |
| Vx   | Apparent volume of distribution (central or peripheral: Vx/F) |

## **Trademark Information**

| Trademarks of the GlaxoSmithKline group of companies |
|--|
| HARP™  |
| METWORXTM  |
|  |

| Trademarks not owned by the GlaxoSmithKline group of companies |  |  |
|--|--|--|
| NONMEM   |  |  |
| R  |  |  |
| SAS  |  |  |
| SIMCYP   |  |  |

## 1. INTRODUCTION

## 1.1. Background

Daprodustat (GSK1278863) is an orally administered small molecule, developed for the treatment of anaemia in CKD patients [1]. Daprodustat is a HIF-prolyl hydroxylase inhibitor (PHI) that has demonstrated the ability to stimulate erythropoiesis and thus increase haemoglobin following oral administration. Several clinical studies have evaluated its pharmacokinetics (PK), safety, and pharmacodynamics in adult healthy participants and CKD patients. The drug has been licensed and commercially available in Japan since August 2020 for the treatment of anaemia in patients with CKD, both on dialysis (D) and not on dialysis (ND) [2].

Currently, there are limited data on the clinical effects of daprodustat in participants <18 years of age. The doses selected for a study in paediatric patients (Study 214066) were based on simulations obtained using a previously developed physiology-based PK model [3], described in Section 1.1.1. In addition, three population PK models in adult patients and healthy participants have also been made available for regulatory submission [4-6] (Section 1.1.2). The population PK models have been revisited in order to analyse collectively the data from the three previously available separate reports, to provide a more comprehensive description of the pharmacokinetic properties of daprodustat (see Section 1.1.3). This model will form the basis for the analysis of pharmacokinetic data in the paediatric patients enrolled into study 214066.

The pediatric study 214066 is an integrated pharmacokinetic and safety open-label basket trial with the aim of assessing the response to treatment of anemia associated with CKD in pediatric participants down to an age of 3 months. Participants might or might not have required dialysis. The enrollment into the study was designed to be staggered by age groups. Initially, adolescent participants (12-<18 years) will be recruited and receive a dose regimen equivalent to that recommended in adult participants (starting dose of 2 mg QD and uptitration based on hemoglobin levels). The study started August 23, 2023. The Sponsor paused recruitment into this clinical study on 16 May 2024 while conducting a review of products and pipeline, whilst only 4 adolescents participants were enrolled into the study. The recruitment pause was not related to any safety concerns. During the recruitment pause, all participants continued the clinical study as per protocol. On 04 September 2024, the Sponsor confirmed that study recruitment would not be re-initiated, and all participants currently enrolled continued the study until the protocol-defined study end. During the study conduct it was foreseen that the outcome of an interim analysis (IA) - based on matching PK and acceptable tolerability of daprodustat - would have provided the elements to: i) continue enrolling adolescents participants to be treated at the same dose levels, and ii) open the enrollment of participant of the subsequent age cohort (6-<12 years), at the corresponding dose foreseen in the protocol (starting dose 1 mg QD). The study should have proceeded opening lower pediatric age cohorts after similar IAs checking the appropriateness of the proposed dosing regimens.

The analyses described in this study data analysis plan (SDAP) will therefore be based on the outcome obtained in these 4 adolescent participant date and has the aim to i) confirm or refine the dosing regimen to be used in the adolescent participants and ii) describe the pharmacokinetics of daprodustat in adolescent participants based on post-hoc estimates of the previously developed population PK model.

## 1.1.1. Previous Population PBPK Model

A physiologically-based pharmacokinetic (PBPK) model (using the SimCyp® v20.0) of daprodustat (GSK1278863) was developed [3] that successfully predicted pharmacokinetic profiles and parameters across multiple clinical studies in healthy participants. Of note, daprodustat PK in healthy participants and participants with CKD did not show important differences based on the covariate analyses of the population PK models (see Section 1.1.2).

Daprodustat is primarily metabolized by cytochrome P450 (CYP) 2C8 with a minor contribution by CYP3A4. In addition to phase 1 studies in healthy participants, clinical drugdrug interaction (DDI) studies with gemfibrozil (potent CYP2C8 inhibitor) and trimethoprim (weak CYP2C8 inhibitor) were used to identify the relative importance of CYP2C8 pathways in the PBPK model and set relevant pharmacokinetic parameters in the PBPK model. The PBPK model was qualified and verified and demonstrated to be robust and accurate to extrapolate dosing regimens to be adopted in paediatric participants. In particular, PBPK simulations were performed (Simcyp® default), to assess the doses to be used in pediatric participants of different age ranges necessary to match the systemic exposures to daprodustat of adults receiving 2 mg oral single dose. The ratios to adult doses to be adopted in pediatric participants, expected to match the PK doses are reported in Table 1.

Table 1. PBPK-Defined Doses in Participants of Different Age Ranges Necessary to Match the Systemic Exposures to Daprodustat of Adults receiving 2 mg Oral Single Dose

| Age Group a | Dose (mg) | Ratio to Adult Dose |
|------------------------|-----------|---------------------|
| >18 years              | 2.0       | N/A                 |
| 12 to <18 years        | 2.0       | 1                   |
| 6 to <12 years         | 1.0       | 1/2                 |
| 2 to <6 years          | 0.50      | 1/4                 |
| 3 months to <2 years   | 0.25      | 1/8                 |

a. PBPK Simulations conducted with 50 Trials of 10 participants consisting of Pediatric participants falling into the specified age buckets (50% females).

## 1.1.2. Previous Population PK Models

Initially, a population PK model for daprodustat was developed using data obtained from Phase 1 studies in healthy participants. The analysis population was later expanded to include CKD patients enrolled in Phase 2 studies, incorporating PK measurements obtained during dialysis and considering the effects of co-medications [4].

[figure not shown]
A 3-compartment distribution model with first order elimination described the disposition of daprodustat (Figure 1). The complex and delayed absorption kinetics following tablet administration was characterized using 2 serial transit compartments, with saturable release from the second into the central compartment when daprodustat was administered in fasted conditions. A 4-compartment transit model with saturable release from the fourth into the central compartment was used to describe the PK data under fed conditions.

Allometry was applied to all clearance and volume terms using standard exponents (fixed to 0.75 and 1.00, respectively) to account for the effect of body weight on daprodustat PK. Other covariate effects included reduced clearance (CL) in the HD population and with co-

Page 8 of 22

administration of the cytochrome P450 (CYP) 2C8-inhibitor gemfibrozil, increased relative bioavailability (F1) with gemfibrozil, and a decreased saturable rate of absorption with food intake (Study PHI113634) [4]. Additionally, differences in the absorption model and in peripheral parameters were identified with mild and moderate hepatic impairment (HI) [4]. The PK of metabolites were fitted *a posteriori* via a stepwise approach, using the final Phase 1 daprodustat PK model as parent input [4].

Figure 1 Structure of the Phase 1 Daprodustat PK Model (Fast Condition)

Abbreviations: CL = apparent clearance (CL/F); ka = absorption rate constant; km = dose amount at half-maximal absorption; km = apparent inter-compartmental clearance (km); km = transit compartment; km = maximal absorption rate; km = apparent volume of distribution (central or peripheral: km). From [4].

External validation using the above Phase 1 model appropriately described the Phase 2 data but underpredicted variability. An exploratory evaluation of potential covariate effects was therefore considered more informative than a formal model-based approach. In Phase 2 participants, co-administered clopidogrel or phosphate binder, African-American race, and sex were detected as statistically significant covariates [4].

The Phase 1 daprodustat model was then applied to the prediction of PK data from Japanese CKD patients in Phase 3 clinical studies [5]. In this analysis, the structural model remained the same as that for the Phase 1 analysis, assuming fed conditions (N=7 transit compartments). All parameters were fixed to that in the Phase 1 model, except for ka, KM, F1, and residual error to achieve an acceptable fit in Phase 3 participants. In addition, the effect of HD was not required and was removed from the model.

Lastly, an independent model was developed to describe the PK of daprodustat using data from Phase 2/3 studies in CKD patients receiving HD, PD, or no dialysis (ND) [6]. The structural base model was consistent with that for Phase 1 and comprised a 3-compartment disposition and transit compartment (N=5) absorption. In contrast to previous models, the data did not support estimation of food effects or saturable release (maximum dose 48 mg vs. 300 mg in Phase 1) on absorption parameters. Covariate effects included a reduction in CL with clopidogrel use, and higher ka in non-dialysis dependent participants.

A comparison of parameter estimates from daprodustat population PK models is provided in Table 1 (Appendix).

## 1.1.3. Comprehensive Population PK Model

The above models independently described the PK characteristics of daprodustat across specific sub-populations using approaches that included the estimation of all parameters, or sequential modelling to quantify covariate effects. However, a population PK model that fits all currently available data in adults was lacking, which might lead to queries in future interactions with regulatory agencies. In addition, the availability of such a model, in which the effects of intrinsic and extrinsic factors are characterised in an integrated manner, will provide the basis for further use of the model to support additional studies, including that in paediatric patients.

Therefore, the datasets used for developing the models described in Section 1.1.2 are being collectively reanalysed, with the intention to revisit some of the model elements described below:

- Absorption, base model:
  - The number of transit compartment to be used for describing absorption in different conditions (Japanese participants, fed and fast conditions) and the need for the nonlinear absorption terms are being assessed.
- Disposition, base model
  - o Effect of body size (body weight, e.g., via estimation of allometric coefficients) is being reassessed.
- Covariates model
  - o In addition to body weight, which will be examined also in the light of the emerging pediatric study, relevant covariates highlighted in the previous analyses are being maintained in the model and their effects are being reassessed (food effect on Vmax, dialysis type on ka and CL, gemfibrozil on F1 and CL, clopidogrel on F1 and CL, CYP2C8 inhibitors on CL,HI on peripheral parameters, African-American race on CL) based on the collective data. Other covariates of clinical interest (age, sex, race, region, CKD status, glomerular filtration rate, CYP2C8 inducers, active dialysis) are being explored.

## 1.2. Analysis Rationale

The analysis described in the present Study Analysis Plan (SDAP) aims to:

- i) assess the daprodustat PK data emerging from the pediatric study, with the intention to describe the pharmacokinetics of daprodustat in adolescent participants who have evaluable PK data.
- ii) Considering that the study was stopped after enrolment of the first 4 adolescent participants, who were the only participants concluding the study, the analyses also aim to confirm the dosing regimen to be used in cohorts of subjects of adolescents. For this aim, the available daprodustat plasma concentrations (dosenormalized as required) will be projected in a plot together with the reference

Page 10 of 22

plasma concentrations observed in adult participants, defined *via* the PBPK simulation exercise (95%PI) [3]. If ≤50% of observations are outside the prespecified reference levels, the dose algorithm proposed for adolescents will be considered adequate. If instead >50% of observations are outside the prespecified reference levels, model-based simulations based on the population PK model and/or PBPK model may be performed to propose alternative starting dosing regimens, able to more appropriately match the exposures observed in adult participants. The adoption of the starting alternative dosing regimen should be sufficiently flexible considering i) the available dosing strengths, and that ii) daprodustat doses will be anyway modulated using the emerging Hemoglobin data.

This modelling exercise will concern the parent drug, daprodustat. As far as metabolites are concerned, a minimal contribution to daprodustat pharmacology cannot be excluded, but the available information indicate that metabolite contribution to clinical effects is minimal. Indeed, in a cocktail study in mice, the key metabolites of daprodustat showed negligible effect on haemoglobin, haematocrit, and red blood cell count compared to unchanged daprodustat. The PK of metabolites is thus considered out-of-scope in the modelling of paediatric data. Metabolite concentration data will be collected in the paediatric study, but they will simply be described using descriptive statistics.

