Drug-drug interactions	Daprodustat is a substrate of CYP2C8. Co-administration of daprodustat with the strong CYP2C8 inhibitor, gemfibrozil increased the maximum plasma concentration (C max ) and area under the curve (AUC) of daprodustat, 4- and 19-fold, respectively, while co-administration of the weak inhibitor, trimethoprim increased the C max and AUC of daprodustat by 1.3- and 1.5-fold, respectively.  Population PK analysis from completed Phase 2 studies suggests that co-administration of daprodustat with a moderate CYP2C8 inhibitor (clopidogrel) leads to a ~2-fold increase in AUC, with no clinically significant increase in the measured Hgb response. Although CYP2C8 induction studies were not performed, co-administration of daprodustat with an inducer of CYP2C8 (e.g., rifampin/rifampicin) may decrease the exposure of daprodustat.	
 
Co-administration of daprodustat with strong CYP2C8 inhibitors, (e.g., gemfibrozil) and inducers, (e.g., rifampin/rifampicin) is not permitted as outlined in Section 5.2 and Section 6.8.1.
 
Specific guidance on the management of potential drug-drug interactions and concomitant medications is provided in Section 6.8 and Section 7.1.
 

214066 Protocol Amendment 02

Potential Risk of Clinical Significance	Summary of Data/Rationale for Risk	Mitigation Strategy
Death, myocardial infarction (MI), stroke, heart failure (HF), thromboembolic events, thrombosis of	Marketed rhEPO/ESAs have been associated with an increased risk for death and serious cardiovascular events when used in patients with anemia of CKD. Clinical studies with marketed rhEPO/analogues have suggested "higher" target Hgb, rate of Hgb rise of greater than 1 g/dL in any 2-week period, and/or higher doses may contribute to these risks.  Daprodustat has been shown to be non-inferior to ESAs in terms of first occurrence of major adverse	
 
Hgb will be closely monitored throughout the dosing period as outlined in the SoA in Section 1.3.
 
Specific guidance for (permanent or temporary) discontinuation of daprodustat based on achieved Hgb is provided in Section 7.1.
 
Monitoring of emerging safety data by an internal GSK Safety Review Team and an IDMC.
 
Specific eligibility criteria related to cardiovascular risk are outlined in Section 5.2.
 
Hgb will be closely monitored throughout the dosing period as outlined Section 4.6.
 

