## 5.2. Confirmation of Dosing Regimen in Adolescent Participants

[figure not shown]
The criterion used for exploring the consistency between simulated data in adults and plasma concentration data in the available adolescents participants will be that >50% of the observed concentrations in the specified age group of pediatric participants is included in the 95% prediction intervals of the simulated data in adults at 2 mg.

The 95% prediction intervals of the simulated data in adults are shown in Figure 2 (together with simulated observations in a panel of 4 participants); 95% prediction intervals of adult daprodustat plasma concentrations following repeated dose of 2 mg are also reported in Table in the Appendix.

If the consistency between predicted and observed concentration data will be ensured (see Figure 2, where only 4 out of 16, i.e., 25% of the observed plasma concentrations are outside the predefined prediction intervals), the outcome of the previously defined pediatric simulations can be considered adequate. Therefore, it can be concluded that the dosing regimen proposed in adolescents (equivalent to that applied to adult participants) is reasonable. Based on this information, it might also be inferred that the starting dose foreseen by the protocol for participants 6-<12 years old (starting dose of 1 mg QD subsequently titrated based on hemoglobin levels) is reasonable.

If the consistency between observations and predictions will not be ensured, then the popPK model (see Section 5.1) may be used (after suitable modifications, as required) to propose a different dose to be used in adolescents and/or in participants in the lower pediatric age ranges.

Figure 2. Overlay of Simulated Daprodustat Plasma Concentrations in Virtual Pediatric Participants after Repeated Dosing of Daprodustat (Normalized to a Dose of 2 mg QD) on the 95% Prediction Interval of Daprodustat Plasma Concentrations in Adults [3].

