| IIV F1 (%CV)                   | 27.9    | 26.3       | 30.9  | 27.9*   |                    | 26.3    |  |
| IIV KM (%CV)                   | 69.0    | 61.0       | 69.5  | 69.0*   |                    | 61.0    |  |
| Residual error                 |         |            |       |         |                    |         |  |
| Proportional (SD)              | 0.470   | 0.471      | 0.469 |         |                    | 0.635   |  |
| Proportional Fed (SD)          |         | 0.556      |       |         |                    |         |  |
| Proportional HI (SD)           |         |            | 0.418 |         |                    |         |  |
| Proportional Phase 2 (SD)      |         |            |       | 0.702   |                    |         |  |
| Log-additive (except Phase 2b) |         |            |       |         | 0.979              |         |  |
| Log-additive (Phase 2b)        |         |            |       |         | 1.63               |         |  |

\* Grey text represents fixed parameters.

Abbreviations: CL = apparent clearance (CL/F); CV = coefficient of variation; HD = haemodialysis; HI = hepatic impairment; ka = absorption rate constant; KM = dose amount at half-maximal absorption; ND = no dialysis; PD = peritoneal dialysis; Qx = apparent inter-compartmental clearance (Qx/F); Tr = transit compartment; Vmax = maximal absorption rate; Vx = apparent volume of distribution (central or peripheral: Vx/F).

Table 2 Daprodustat Plasma Concentrations after Repeated 2 mg QD in Adults, Simulated by PBPK

| Time (h) | Percentiles |          |          |  |  |  |  |  |  |
|----------|-------------|----------|----------|--|--|--|--|--|--|
|          | 2.5th       | 50th     | 97.5th   |  |  |  |  |  |  |
| 0        | 0.000391    | 0.005865 | 0.10584  |  |  |  |  |  |  |
| 0.25     | 0.78103     | 3.661475 | 13.28695 |  |  |  |  |  |  |
| 0.5      | 3.473855    | 13.19735 | 39.28452 |  |  |  |  |  |  |
| 0.75     | 6.108987    | 22.33292 | 60.27049 |  |  |  |  |  |  |
| 1        | 6.712179    | 27.77886 | 73.10667 |  |  |  |  |  |  |
| 1.5      | 6.033509    | 28.84642 | 88.58097 |  |  |  |  |  |  |
| 2        | 3.770527    | 21.71046 | 86.0139  |  |  |  |  |  |  |
| 2.5      | 2.36174     | 15.25755 | 72.75431 |  |  |  |  |  |  |
| 3        | 1.382509    | 9.456743 | 57.22533 |  |  |  |  |  |  |
| 4        | 0.497801    | 3.47939  | 36.25722 |  |  |  |  |  |  |
| 5        | 0.18857     | 1.346953 | 21.57169 |  |  |  |  |  |  |

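### Passing the PK plan's 50% rule rules out gross misfit only; it cannot by itself support matched adult exposure in adolescents, or the inference for ages 6 to <12 years

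*SAP*

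**What the plan says.** PK plan 1.2 compares the available daprodustat concentrations, dose-normalised as required, with the adult PBPK 95% prediction interval and concludes: "If ≤50% of observations are outside the prespecified reference levels, the dose algorithm proposed for adolescents will be considered adequate". It adds that "daprodustat doses will be anyway modulated using the emerging Hemoglobin data".

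PK plan 5.2 states the criterion the other way round, as ">50% of the observed concentrations in the specified age group of pediatric participants is included in the 95% prediction intervals". Its worked example, built on simulated values, treats consistency as met where "only 4 out of 16, i.e., 25% of the observed plasma concentrations are outside the predefined prediction intervals". After a pass, "it can be concluded that the dosing regimen proposed in adolescents (equivalent to that applied to adult participants) is reasonable", and "it might also be inferred that the starting dose foreseen by the protocol for participants 6-<12 years old" is reasonable too.

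The limits are in PK plan Appendix Table 2, "Daprodustat Plasma Concentrations after Repeated 2 mg QD in Adults, Simulated by PBPK". Protocol 4.4.2 and 9.3.1 and SAP 12.1 use the same 50% as the point above which the PBPK model is updated. Protocol 9.3.1 and SAP 12.1 take paediatric or current-age-group simulations as the reference; PK plan 5.2 takes adults.

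**The concern.** About 5% of concentrations should fall outside a correct 95% prediction interval, yet the rule reacts only at around half. The interval is wide and the sample is small, so a pass may say little about whether adolescent exposure is close to adult exposure, which is the stated purpose of the dose scaling. No exposure ratio, margin or operating characteristic accompanies the rule.

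At stake is what the report concludes about the adolescent regimen, and what it implies for an age group with no data.

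**Working it through.** **The plan's own figure.** 4/16 = 25%, with 16 = 4 participants × 4 steady-state samples (Protocol 1.3, footnote k). The documents give no error rate for the rule, so there is nothing else to reproduce.

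**The rule in counts, for 16 samples.** Section 1.2 passes with 8 or fewer outside. Section 5.2 needs more than half inside, so it passes with 7 or fewer outside.

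**Interval width** (97.5th ÷ 2.5th percentile, Appendix Table 2):
- pre-dose: 0.10584/0.000391 = 271
- 0.75 h: 60.27049/6.108987 = 9.9 (narrowest)
- 1 h: 73.10667/6.712179 = 10.9
- 2 h: 86.0139/3.770527 = 22.8
- 6 h: 12.86794/0.081095 = 159

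**A 3-fold higher exposure, by hand.** Assume log concentration at each time is a split normal about the tabulated median. The upper SD is ln(P97.5/P50)/1.96 and the lower SD is ln(P50/P2.5)/1.96. Multiplying every concentration by 3 adds ln 3 = 1.099.

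| Time | ln(P97.5/P50) | minus ln 3 | SD | z | Above limit |
|---|---|---|---|---|---|
| pre-dose | 2.893 | 1.794 | 1.476 | 1.22 | 11.2% |
| 1 h | 0.968 | −0.131 | 0.725 (lower SD) | −0.18 | 57.2% |
| 2 h | 1.377 | 0.278 | 0.702 | 0.40 | 34.6% |
| 6 h | 3.137 | 2.039 | 1.601 | 1.27 | 10.1% |

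Values below the lower limit add about 0.5 points in total. Expected outside: 4 × (0.112 + 0.572 + 0.346 + 0.101 + 0.005) = 4.5 of 16. Failing needs 9 (section 1.2) or 8 (section 5.2).

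**Chance of passing.** Same distribution, sampling times uniform in the protocol windows (pre-dose, 0.5–1.5, >1.5–3, 4–8 h), 40,000 simulated data sets per setting. Ranges span within-participant correlation 0 to 0.8.

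| True exposure ÷ predicted | Mean outside | Pass, section 1.2 | Pass, section 5.2 |
|---|---|---|---|
| 1 | 5% | about 100% | about 100% |
| 2 or 1/2 | 12–14% | 99–100% | 98–100% |
| 3 | 27% | 94.6–99.2% | 89–97% |
| 1/3 | 22% | 95.9–99.7% | 92–99% |
| 5 or 1/5 | 41–43% | 74–84% | 60–69% |
| 7 | 53% | about 52% | 28–35% |

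Variations on a uniform 3-fold error, section 1.2 wording:
- Post-dose samples only (12, pass at 6 or fewer outside): 89–98.5%.
- Day 1 samples added (28): 92–99.9%.
- Extra log residual of 0.635 or 0.979 (Appendix Table 1): a correct model then puts 11% or 19% outside, and the 3-fold error still passes 93–99%.

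The 25% outside in the plan's example is about what a uniform 3-fold error gives (22–27%). Exactly 8 of 16, where the two wordings disagree, occurs 1–5% of the time at 3-fold.

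**If the error comes from clearance** rather than a uniform shift (3-compartment steady-state curve, Phase 1 healthy parameters, section 1.2 wording): 3-fold higher exposure passes 88–99%. Three-fold lower passes 70–79% with saturable release and 32–37% with first-order release. Five-fold lower passes 0.2–13%.

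**Shrinkage, which bears on any ratio reported beside the rule.** PK plan 5.1 starts from adult parameters held fixed (MAXEVAL=0). With 4 samples, the weight on a participant's own data is roughly w = ω²/(ω² + σ²/4), and a true ratio of 3 appears as 3^w.
- Phase 1 healthy values (CV 16.8%, ω = 0.167; σ = 0.47): w = 0.0279/(0.0279 + 0.0552) = 0.34, so the ratio appears as about 1.4.
- Phase 2/3 values (CV 75%, ω = 0.668; σ = 0.979): w = 0.446/(0.446 + 0.240) = 0.65, so about 2.0.

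**The case against.** **The pass rates depend on assumptions.** The uniform shift, the distribution shape and the correlation are not in the documents. A reader might infer that the rule misses large errors of every kind. The documents do not support that: a large clearance-driven fall in exposure could often be caught, and how often depends on the absorption model, which PK plan 1.1.2 leaves unsettled. This limits the finding for under-exposure.

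**The rule is not new.** A reader might infer that the PK plan turned a model-update trigger into an acceptance rule. Protocol 4.4.2 already says that data in line with the predictions leave the planned starting dose in place. What is missing from the PK plan's conclusion is the haemoglobin and safety review that the IDMC would have added under Protocol 4.7.

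**The language is partly soft.** Section 5.2 speaks of exploring consistency and of a reasonable regimen, and section 2 of providing support. Section 1.2 is not hedged. Population PK modelling is planned too, but it is not part of the pass rule, and section 5.2 turns to it for dosing only when the check fails.

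**The clinical consequence is small.** A reader might infer that participants are at risk, or that the adolescent dose is wrong. Neither follows. Recruitment will not restart (PK plan 1.1), doses are titrated on haemoglobin, and Protocol Table 3 reports that a moderate CYP2C8 inhibitor "leads to a ~2-fold increase in AUC, with no clinically significant increase in the measured Hgb response". That statement covers about 2-fold, not 3-fold. Titration limits harm, but it is not evidence that exposure matches.

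**Only four participants are available.** True, and that is a reason for a weaker conclusion.

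**Conclusion.** The point stands in a limited form. Under a uniform proportional shift, and across both wordings of the rule, a 3-fold exposure error passes about 89–99.7% of the time and a 5-fold error about 60–85%. These figures rest on the split log-normal from Appendix Table 2 and within-participant correlation of 0 to 0.8, and they do not carry over to large clearance-driven under-exposure. The qualitative conclusion does not need the exact figures: an interval at least 10-fold wide, with a threshold near 50% where about 5% is expected, detects gross misfit only. A pass therefore cannot by itself support matched adult exposure in adolescents, and still less an inference for ages 6 to <12 years. The effect is on the reported conclusion, not on patient management.

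**What to change.** 1. In PK plan 1.2 and 5.2, describe the percentage outside as a descriptive check and show it by sampling window, since the early window carries most of the information. Replace the adequate and reasonable conclusions with wording such as: *no gross departure from the adult prediction interval was seen; with 4 participants, matching of adult exposure cannot be concluded.*
2. Remove the inference for ages 6 to <12 years, and do not present 4 of 16 outside as showing consistency.
3. Use one rule at exactly 50%, and name one reference interval, reconciling PK plan 5.2 with Protocol 9.3.1 and SAP 12.1.
4. Optional: report the adolescent/adult geometric mean ratio of dose-normalised steady-state AUC and Cmax with a 95% CI, in keeping with the PK estimand in Protocol 3.1. Do this only if clearance is estimated from the adolescent data or the estimates are otherwise unshrunken. Read the AUC ratio against the PBPK-predicted 31.7/25.3 = 1.25 (Protocol Table 5) as well as against 1. Do not build the CI on MAXEVAL=0 post-hoc estimates, which are pulled toward adult values.

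Items 1 to 3 are wording only and need no new data; with recruitment ended, no protocol amendment is needed. The price is a weaker stated conclusion. No dose is proposed.
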